#### Assessment Procedures

After basic screening, assessments will be conducted by trained social services staff and peer supporters employed by NGOs for the intervention group, and by trained research assistants employed by the University of Hong Kong for the control group.

For the intervention group, assessments will be conducted at baseline (T0/Intake), completion of intervention (4 weeks to 6 months, depending on individual condition) or drop-out (T1/Exit), and follow-up at 12 months (T2/FU). For control group, assessment would be conducted at T0 and T2.

Assessment for those with clinically significant depressive symptoms will last for about 90 minutes, and assessment for those at-risk of depression will last for around 60 minutes.

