### Participants

1. Intervention Group: older people at-risk of having depression (n=1,600) and those with clinically significant depressive symptoms (n=400) recruited from NGOs providing the intervention in four pilot districts in Hong Kong
2. Control Group: older people at-risk of having depression (n=400) and those with clinically significant depressive symptoms (n=100) referred by different NGOs in Hong Kong and recruited through open recruitment

The inclusion criteria are:

- age 60 years or above; and
- residing in Kwun Tong, Kwai Chung, Tseung Kwan O, or Sham Shui Po; and
- have one or more known risk factor(s) for developing depression; and/or
- have depressive symptoms of mild level or above; and
- able to give informed consent to participate

The exclusion criteria are:

- known history of autism, intellectual disability, schizophrenia-spectrum disorder,
- bipolar disorder, Parkinson's disease, or dementia
- (temporary exclusion criteria) imminent suicidal risk;
- and difficulty in communication

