#### Interventions

The intervention group will receive a collaborative stepped care programme provided by registered social workers and trained peer supporters from elderly or mental health service units (NGOs) according to level of risks, symptom severity, and intervention response. Home visits or other format of contact will be delivered by trained peer supporters employed by NGOs to detect and engage hidden cases.

For “at-risk” group, 4 weeks of “selective prevention” group sessions will be provided at the elderly service level by trained peer supporters with registered social worker supervision, on wellness topics tailored to the person’s concern as entry point, packaged with mental health information, followed by a review. If the review shows no significant improvement, a further 2-4 weeks of group plus individual casework sessions will be provided.

For people with depressive symptoms, we further divide them to “mild” and “moderate” groups. For mild group, 6-8 weeks of indicated prevention with psychoeducation or low-intensity psychotherapy would be provided. For moderate group, 6-8 weeks high- intensity cognitive behavioral therapy (CBT) would be provided. All intervention for depressed elderly would be conducted by registered social workers who are trained by this project and employed by the NGOs. The trained peer supporters will be matched to individual older adults to walk them through the process.

The control group will receive treatment as usual, which will be determined by the responsible worker from NGO units.

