9. EQ-5D-5L (Herdman et al., 2011): a measure of health-related quality of life at five dimensions (5D), each with five levels (5L) of problems, and the five dimensions are: mobility, self-care, usual activities, pain/discomfort, and anxiety/depression. The traditional Chinese version for Hong Kong developed by EuroQol Group would be used.
10. Lifeengagement: a semi-structured interview asking clients about their typical day activities in three domains, physical, social, and mental. A combination of being active in at least two domains would be used as one of the exit criteria.
11. Client Service Receipt Inventory (CSRI) (Chisholm et al., 2000): to collect the current types and level of services which comprise the care package of each participant, and a locally adapted short version would be developed for this purpose.

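### Assessor type coincides with arm, and the plan permits a helper to assess their own client at 12 months; separate the two roles at T2, holding assessor role constant

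*Combined protocol and SAP*

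**What the plan says.** Assessment Procedures divides the assessors by arm. In the intervention arm, "assessments will be conducted by trained social services staff and peer supporters employed by NGOs for the intervention group". The other arm is assessed "by trained research assistants employed by the University of Hong Kong for the control group". No crossover is described at any time point.

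The intervention arm is assessed at T0, at exit or drop-out (T1) and at 12 months (T2). "For control group, assessment would be conducted at T0 and T2", so T2 is the only post-baseline comparison between arms.

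Interventions gives the delivery roles. For the at-risk group, "group sessions will be provided at the elderly service level by trained peer supporters with registered social worker supervision". For the others, "All intervention for depressed elderly would be conducted by registered social workers who are trained by this project and employed by the NGOs". The same paragraph adds: "The trained peer supporters will be matched to individual older adults to walk them through the process".

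Data Analysis plans a three-level linear mixed model for change in outcomes, including PHQ-9 and GAD-7, with a Satterthwaite correction because clusters are few. It names no assessor term. The only safeguard stated for assessors, in either arm, is that they are trained. The available text contains no blinding and no rule that keeps the treating worker or matched peer away from their own client's assessment.

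**The concern.** Peer supporters are named both as helpers and as assessors. Social workers who treat and social services staff who assess all work for NGOs. A participant may answer a person who has helped them differently from a stranger. Answers may be kinder, which would flatter the programme, or franker, which would hide a benefit. Neither possibility exists in the control arm, where the assessors are university assistants with no described part in care.

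At stake is the PHQ-9 and GAD-7 change contrast, which carries the efficacy objective. A helper-related shift present at T2 would enter that contrast as if it were a programme effect, and the data could not reveal it afterwards.

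**Working it through.** The plan gives no power figure, SD, intracluster correlation or drop-out rate, so there is no stated figure to reproduce. The check has two parts.

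**1. What cancels and what does not.** Let a be the constant NGO assessor effect, c the constant university effect, s a shift arising only after help has been given, and p the share of the intervention arm that carries s at T2.

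- Intervention change = true change + (a + p·s) − a = true change + p·s
- Control change = true change + c − c = true change
- Difference in change = programme effect + p·s

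The constants a and c drop out and p·s stays. Could a model term remove it? Take the columns intercept, arm, assessor type, time, arm × time and assessor × time, under the plan's assessor rule:

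- Control T0: 1, 0, 0, 0, 0, 0
- Control T2: 1, 0, 0, 1, 0, 0
- Intervention T0: 1, 1, 1, 0, 0, 0
- Intervention T2: 1, 1, 1, 1, 1, 1

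Columns 2 and 3 are identical, as are columns 5 and 6. The rank is 4 of 6, so assessor × time cannot be told apart from arm × time.

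**2. How large it could be (illustration).**

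- From Participants: 1,600 + 400 = 2,000 intervention and 400 + 100 = 500 control.
- From Data Analysis: significance level 0.05, taken as two-sided.
- Assumed: no true effect, s = 0.5 PHQ-9 points still present at T2, SD of change 4, design effect (DE) 2 or 4, and p = 20%, 50% or 100%.

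Only the 20% is tied to a document figure: 400/2,000, the intervention participants described as "those with clinically significant depressive symptoms (n=400) recruited from NGOs providing the intervention".

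SE = SD × √[DE × (1/n₁ + 1/n₂)]

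- DE 2: 4 × √[2 × (1/2000 + 1/500)] = 4 × √0.005 = 0.283
- DE 4: 4 × √[4 × 0.0025] = 0.400
- DE 2 with 30% missing at T2 (1,400 v 350): 0.283/√0.7 = 0.338

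Average bias p·s: 0.2 × 0.5 = 0.1; 0.5 × 0.5 = 0.25; 1 × 0.5 = 0.5.

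Rejection rate = P(|Z| > 1.96), where Z has mean p·s/SE and variance 1. At DE 2 the means are 0.354, 0.884 and 1.768.

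| Scenario | p = 20% | p = 50% | p = 100% |
|---|---|---|---|
| DE 2 | 6.4% | 14.3% | 42.4% |
| DE 4 | 5.7% | 9.6% | 24.0% |
| DE 2, 30% missing | 6.0% | 11.5% | 31.6% |
| DE 2, SD 3 | 7.6% | 21.8% | 65.4% |
| DE 2, SD 5 | 5.9% | 10.9% | 29.3% |

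The planned test uses Satterthwaite degrees of freedom, and the plan gives no number. With 6 assumed, the critical value is 2.45 and the noncentral t distribution gives 6%, 12% and 32% in the DE 2 row.

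If the depressive-symptom stratum were analysed alone (400 v 100, all carrying 0.5), SE = 0.632 at DE 2 and 0.894 at DE 4, giving 12.4% and 8.6%. The plan specifies no such analysis.

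A shift of the opposite sign gives the same rejection rates when there is no effect, now against the programme. When there is a true benefit, it takes p·s off the estimate.

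**The case against.** The strongest reply is that the plan never says a helper assesses their own client. A reader might infer that it does, or that the social services staff who assess are the registered social workers who treat. The text supports neither inference: it names peer supporters in both roles, does not say that any individual holds both for the same participant, and leaves the link between the two staff titles open. This stands, and the point is limited to what the plan permits.

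A reader might also infer that the whole NGO-versus-university difference biases the result. It does not bias the change analysis, because any constant part cancels.

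The larger rates need half or all of the 2,000 to carry a lasting shift. Yet 1,600 of them are at-risk participants whose initial programme is four weeks of group sessions, and the matching sentence sits in the paragraph on depressive symptoms, so its reach is unclear. T1 is at most six months; if T1 and T2 both count from intake, T2 falls at least six months after exit and the shift may have faded. The normal approximation also overstates the upper figures relative to the planned small-sample correction. All of this stands, and it pulls the likely size down.

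Two replies do not settle the matter. The quasi-experimental design explains non-random allocation, but it does not require helpers to assess their own clients. That the scales record participants' answers is no protection either: the shift described is in the answer, not in a rater's judgement, and the mode of administering PHQ-9 and GAD-7 is not stated.

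A remedy that merely sends any other NGO employee would let the role change from peer supporter to social services staff, or the reverse, between T0 and T2 in one arm only. That would undo the cancellation, so role must be held constant.

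**Conclusion.** The point holds as a design weakness of uncertain size that should be corrected because the remedy is cheap. Two facts are firm on the text: assessor type equals arm, and nothing in the available text keeps a helper from assessing their own client at T2. It follows that a post-treatment assessor shift could not be separated from the programme effect.

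The size is not established. On the assumptions above, the false-positive rate runs from about 6%, at the one share tied to a document figure, to 42% if everyone carries the shift, or 32% with 6 assumed degrees of freedom. The 42% should not be read as this trial's error rate: shift, persistence, share, SD and design effect are all assumed, and the direction could be the reverse. Confidence is high on the structure and low on the magnitude.

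**What to change.** Add to Assessment Procedures: 'At T2, no worker or peer supporter assesses a participant they treated or were matched to. Another existing NGO staff member of the same role (social services staff or peer supporter) as the T0 assessor does so. Assessor role, and whether the assessor treated or was matched to the participant, are recorded at T0 and T2, and exceptions are logged.'

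Add to Data Analysis: a sensitivity analysis of PHQ-9 and GAD-7 without the logged exceptions, and a statement that the remaining NGO-versus-university aliasing is a limitation.

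T2 should stay with NGO staff. Moving only the intervention arm's T2 to university assistants would stop the constant difference from cancelling. T1 stays as planned: it has no control counterpart and serves the programme's exit decision (under Measurements, on the life-engagement interview: "A combination of being active in at least two domains would be used as one of the exit criteria").

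The cost is rostering within existing staff, with no added visits. It is harder in small centres, and T2 completion may fall slightly when the familiar helper does not conduct the visit; the logged exception is the fallback for both. The change does not remove answers shaped by loyalty to the NGO as a whole.

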#### Interventions

The intervention group will receive a collaborative stepped care programme provided by registered social workers and trained peer supporters from elderly or mental health service units (NGOs) according to level of risks, symptom severity, and intervention response. Home visits or other format of contact will be delivered by trained peer supporters employed by NGOs to detect and engage hidden cases.

For “at-risk” group, 4 weeks of “selective prevention” group sessions will be provided at the elderly service level by trained peer supporters with registered social worker supervision, on wellness topics tailored to the person’s concern as entry point, packaged with mental health information, followed by a review. If the review shows no significant improvement, a further 2-4 weeks of group plus individual casework sessions will be provided.

For people with depressive symptoms, we further divide them to “mild” and “moderate” groups. For mild group, 6-8 weeks of indicated prevention with psychoeducation or low-intensity psychotherapy would be provided. For moderate group, 6-8 weeks high- intensity cognitive behavioral therapy (CBT) would be provided. All intervention for depressed elderly would be conducted by registered social workers who are trained by this project and employed by the NGOs. The trained peer supporters will be matched to individual older adults to walk them through the process.

The control group will receive treatment as usual, which will be determined by the responsible worker from NGO units.

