### Data Analysis

We will generate descriptive statistics of the demographic and clinical variables at the baseline (T0/Intake) assessment. The independent sample t-test will be used to compare the means of continuous variables in the intervention and control groups; the chi-square test will be used to compare categorical variables; and Fisher exact test will be used for variables with low cell counts ( $n < 5$ ). For the majority of clinical scales that are ordinal in nature, the independent samples Mann-Whitney U-test will be used to examine whether the same distributions could

be assumed across groups. As observations at two /three time points are nested within individuals and individuals are nested within clusters (centers), changes in outcome measures, including PHQ-9 and GAD-7 scores, will be assessed by a three-level linear mixed model. Because the number of clusters is small, degree-of-freedom correction using the Satterthwaite method will be applied to the mixed models to maintain the desired type I error rate (Leyrat, Morgan, Leurent, & Kahan, 2017). We will use STATA 14.1 (StataCorp, 2015) for data analysis. For all the tests, the statistical significance level was set at .05.

To investigate engagement in the intervention versus control group, the following analyses will be conducted: (1) Cox proportional hazard regression analysis of the time to the primary endpoint of voluntary withdrawal from service; (2) Chi-square test of initial refusal of service by eligible participants after screening.

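### At-risk intervention participants are treated in peer-led groups, but the mixed model has no session-group level; unless the centre term covers change over time, standard errors are somewhat too small

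*Combined protocol and SAP*

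**What the plan says.** The Participants section plans an intervention arm of "older people at-risk of having depression (n=1,600) and those with clinically significant depressive symptoms (n=400) recruited from NGOs providing the intervention", and a control arm of "older people at-risk of having depression (n=400) and those with clinically significant depressive symptoms (n=100) referred by different NGOs in Hong Kong", some of them openly recruited.

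The Interventions section describes four weeks of selective prevention for the at-risk stratum: "group sessions will be provided at the elderly service level by trained peer supporters with registered social worker supervision". For those who do not improve, "a further 2-4 weeks of group plus individual casework sessions will be provided". For the symptomatic stratum, "All intervention for depressed elderly would be conducted by registered social workers who are trained by this project"; whether that is individual or group work is not stated. Controls receive usual treatment as decided by the NGO worker, with no format given.

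The Data Analysis section specifies a three-level linear mixed model: repeated observations within persons, and "individuals are nested within clusters (centers"). It applies a Satterthwaite correction because clusters are few. It does not give the number of centres, say whether any random effect applies to change over time, or mention session groups or peer supporters. No identifier for either appears under Measurements.

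**The concern.** The plan justifies its mixed model by nesting, yet leaves out a level of nesting that its own intervention creates. People in one session group share a peer supporter and fellow members, so their outcomes after baseline may be correlated. That correlation starts after T0. A person or centre intercept that is constant across visits cancels from the change since T0 and cannot carry it.

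If nothing else in the model picks it up, the change in the intervention arm is reported with too much precision. Confidence intervals are then too short and the 5% level is exceeded. A within-arm change suffers most, because no control variance dilutes the problem. Under Assessment Procedures, T1 exists only in the intervention arm, so any T0-T1 change is of that kind. Group membership may also be unrecoverable later if it is not recorded at allocation.

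**Working it through.** The plan gives no power, design-effect or precision figure to reproduce, so the check compares the SE that the model would report with the SE that holds when session groups matter.

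**From the documents.** Intervention: 1,600 at-risk + 400 symptomatic = 2,000, so the at-risk share is 1,600/2,000 = 80%. Control: 400 + 100 = 500. Level 0.05, with two-sided testing assumed.

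**Assumed, because not given.** Session-group size m; ICC of change within a session group; correlation in the at-risk intervention stratum only; a model with random intercepts only. Variance is set to 1, since only ratios matter.

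**Formulas.**
- Design effect: DEFF = 1 + (m − 1) × ICC.
- At-risk contrast: true/model SE = √[(DEFF/1600 + 1/400) / (1/1600 + 1/400)].
- Overall contrast: true/model SE = √[(0.8² × DEFF/1600 + 0.2²/400 + 1/500) / (1/2000 + 1/500)].
- At-risk within-arm change: true/model SE = √DEFF.
- Actual error = 2 × [1 − Φ(1.96/ratio)].

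**Worked case, m = 8, ICC 0.05.** DEFF = 1 + 7 × 0.05 = 1.35. Overall: 0.64 × 1.35/1600 = 0.00054; adding 0.0001 and 0.002 gives 0.00264; divided by 0.0025 this is 1.056, whose root is 1.028. At-risk: (0.00084375 + 0.0025)/0.003125 = 1.07, root 1.034. Within arm: √1.35 = 1.162.

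These formulas hold total variance equal in all groups. If the session-group effect instead adds to the variance of the grouped participants, the between-arm ratios are lower. The table gives both (added variance first), with the actual error in brackets.

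| m | ICC | DEFF | Overall, 2,000 v 500 | At-risk, 1,600 v 400 | At-risk within arm |
|---|---|---|---|---|---|
| 8 | 0.02 | 1.14 | 1.006–1.011 (5.1–5.3%) | 1.008–1.014 (5.2–5.3%) | 1.068 (6.6%) |
| 8 | 0.05 | 1.35 | 1.016–1.028 (5.4–5.6%) | 1.020–1.034 (5.5–5.8%) | 1.162 (9.2%) |
| 10 | 0.05 | 1.45 | 1.024–1.035 (5.6–5.8%) | 1.030–1.044 (5.7–6.0%) | 1.204 (10.4%) |
| 10 | 0.10 | 1.90 | 1.049–1.070 (6.2–6.7%) | 1.059–1.086 (6.4–7.1%) | 1.378 (15.5%) |
| 15 | 0.02 | 1.28 | 1.018–1.022 (5.4–5.5%) | 1.022–1.028 (5.5–5.6%) | 1.131 (8.3%) |
| 50 | 0.05 | 3.45 | 1.172–1.180 (9.5–9.7%) | 1.210–1.221 (10.5–10.8%) | 1.857 (29.1%) |

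The last row stands for clustering by peer supporter, if one person's clients number 50. Between-arm ratios stay small at ordinary group sizes because the 500 controls supply 0.002/0.0025 = 80% of the model variance.

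As a shortfall in the reported SE (1 − 1/ratio), at m = 8 to 10 and ICC 0.05 to 0.10 with equal variances, the at-risk contrast is 3 to 8% short and the at-risk within-arm change 14 to 27% short. For the whole intervention arm, the within-arm ratios are 1.133 to 1.317, a shortfall of 12 to 24%.

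**Does the centre term help?** A simulation (400 runs per setting, 8 centres per arm assumed, centres nested in arm) compared the empirical SD of the arm effect on change with the fitted SE.
- With no centre effect on change in either the data or the model, the ratio was 1.06 (m = 10, ICC 0.05), 1.05 (m = 15, ICC 0.10) and 1.16 (m = 50, ICC 0.05). With 400 runs each ratio carries a relative error of about 1/√800 = 3.5%.
- With a random centre effect on change in the model, the ratio was 0.90 to 0.96, so the SE was not too small: the centre term absorbed the group variance. One setting (m = 10, no centre variance) is left out because singular fits spoiled its mean SE.
- With a true centre-by-time variance of 0.02 (assumed) left out of the model, the ratio was 1.61 to 1.74, far larger than for session groups alone.

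**The case against.** The strongest reply is that a three-level model need not have random intercepts only. If centres vary in change over time, the simulation shows no shortfall. A reader might infer from the missing level that the intervals are certainly too narrow. The documents do not support that, because they leave the random-effects structure open. The same silence means that the protection cannot be assumed.

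A reader might also infer that clustering by group arises in one arm only. The text does not say so: the format of usual care is not described. What stands is that the programme's own group sessions are described only for the intervention arm.

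A third tempting reading is that a T0-T1 test within the intervention arm is planned and badly affected. The Data Analysis section names no such separate analysis, nor a separate at-risk contrast, and the Design section sets out a between-group comparison. The within-arm figures therefore apply only if such changes are reported.

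The size is also open to challenge. Group size and ICC are assumed. The only post-baseline visit that both arms share is at 12 months, long after a four-week group, and topics are tailored to the person; both points argue for a smaller ICC. That is fair, and is why the ICC 0.02 rows belong in the table. Finally, people may attend more than one group, and an extra level with few centres may give singular fits. Both are practical difficulties that the fix must handle.

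**Conclusion.** The point holds in a conditional and modest form. The plan treats 80% of the intervention arm in groups and names no term for them. If the centre term does not cover change over time, standard errors for post-baseline change in that arm are too small.

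For the overall comparison the effect is slight: a true SE about 2 to 4% above the reported one for groups of 8 to 10 at ICC 0.05, and under 2.5% for groups of 6 to 15 if the ICC is 0.02 or less. It becomes material for within-arm changes, or if clustering follows a peer supporter with many clients. All these sizes rest on assumed group sizes and ICCs, random intercepts only, and no comparable clustering among controls. It is a minor repair to the analysis plan and does not undermine the between-arm comparison. The unstated centre-by-time structure may matter more, so the two should be settled together.

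**What to change.** 1. Record a session-group identifier and its peer supporter when an at-risk participant is allocated to a group. If a person attends more than one group, use the first one assigned.
2. In the Data Analysis section, add a random session-group effect on post-baseline visits, for at-risk intervention participants only (partially nested, below centre).
3. In the same model, specify a centre random effect on change over time, and state how openly recruited controls are assigned to a centre.
4. State in advance that if the fit is singular, the session-group term is dropped, the centre-by-time term is kept, and the session-group result is reported as a sensitivity analysis.

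The cost is small: a little extra data capture, a few sentences in the plan, and slightly wider intervals from the session-group term. The centre term can widen them more. In the simulation the fitted SE rose from about 0.050 to between 0.087 and 0.093 where centres truly differed in change, which is real uncertainty. Where they did not differ, it rose from about 0.049 to between 0.058 and 0.064, which is somewhat conservative.
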